9.4.1.2. Dose Adjustments and Delays

9.4.1.2.1. Pembrolizumab

9.4.1.2.1.1. Pembrolizumab Dose Modifications

Adverse events (both nonserious and serious) associated with pembrolizumab exposure may represent an immunologic etiology. These AEs may occur shortly after the first dose or several

months after the last dose of treatment. Pembrolizumab must be withheld for drug-related toxicities and severe or life-threatening AEs as per [Table JFCQ.9.2](#).

Table JFCQ.9.2. Dose Modification Guides for Pembrolizumab Drug-Related Adverse Events

Toxicity	Hold Treatment For Grade	Timing for Restarting Treatment	Treatment Discontinuation
Diarrhea/Colitis	2-3	Toxicity resolves to Grade 0-1	Toxicity does not resolve within 12 weeks of last dose or inability to reduce corticosteroid to 10 mg or less of prednisone or equivalent per day within 12 weeks.
	4	Permanently discontinue	Permanently discontinue
AST, ALT, or Increased Bilirubin	2	Toxicity resolves to Grade 0-1	Toxicity does not resolve within 12 weeks of last dose.
	3-4	Permanently discontinue (see exception below) ^a	Permanently discontinue
Type 1 diabetes mellitus (if new onset) or Hyperglycemia	T1DM or 3-4	Hold pembrolizumab for new onset Type 1 diabetes mellitus or Grade 3-4 hyperglycemia associated with evidence of beta cell failure.	Resume pembrolizumab when patients are clinically and metabolically stable.
Hypophysitis	2-4	Toxicity resolves to Grade 0-1. Therapy with pembrolizumab can be continued while endocrine replacement therapy is instituted	Toxicity does not resolve within 12 weeks of last dose or inability to reduce corticosteroid to 10 mg or less of prednisone or equivalent per day within 12 weeks.
Hyperthyroidism	3	Toxicity resolves to Grade 0-1	Toxicity does not resolve within 12 weeks of last dose or inability to reduce corticosteroid to 10 mg or less of prednisone or equivalent per day within 12 weeks.
	4	Permanently discontinue	Permanently discontinue
Hypothyroidism		Therapy with pembrolizumab can be continued while thyroid replacement therapy is instituted	Therapy with pembrolizumab can be continued while thyroid replacement therapy is instituted.
Infusion Reaction	2 ^b	Toxicity resolves to Grade 0-1	Permanently discontinue if toxicity develops despite adequate premedication
	3-4	Permanently discontinue	Permanently discontinue
Pneumonitis	2	Toxicity resolves to Grade 0-1	Toxicity does not resolve within 12 weeks of last dose or inability to reduce corticosteroid to 10 mg or less of prednisone or equivalent per day within 12 weeks.
	3-4	Permanently discontinue	Permanently discontinue
Renal Failure or Nephritis	2	Toxicity resolves to Grade 0-1	Toxicity does not resolve within 12 weeks of last dose or inability to reduce corticosteroid to 10 mg or less of prednisone or equivalent per day within 12 weeks.
	3-4	Permanently discontinue	Permanently discontinue
All Other Drug-Related Toxicity ^c	3	Toxicity resolves to Grade 0-1	Toxicity does not resolve within 12 weeks of last dose or inability to reduce corticosteroid to 10 mg or less of prednisone or equivalent per day within 12 weeks.
	4	Permanently discontinue	Permanently discontinue

Abbreviations: AE = adverse event; ALT = alanine aminotransferase; AST = aspartate aminotransferase; IRR = infusion-related reaction; T1DM = type 1 diabetes mellitus.

Note: Permanently discontinue for any severe or Grade 3 (Grade 2 for pneumonitis) drug-related AE that recurs or any life-threatening event.

- a For patients with liver metastasis who begin treatment with Grade 2 AST or ALT, if AST or ALT increases by greater than or equal to 50% relative to baseline and lasts for at least 1 week, then patients should be discontinued.
- b If symptoms resolve within one hour of stopping drug infusion, the infusion may be restarted at 50% of the original infusion rate (e.g., from 100 mL/hr to 50 mL/hr). Otherwise, dosing will be held until symptoms resolve and the patient should be given premedication for the next scheduled dose. Refer to [Table JFCQ.9.5 – IRR Treatment Guidelines](#) for further management details.
- c Patients with intolerable or persistent Grade 2 drug-related AE may hold study medication at physician discretion. Permanently discontinue study drug for persistent Grade 2 adverse reactions for which treatment with study drug has been held, that do not recover to Grade 0-1 within 12 weeks of the last dose.

9.4.1.2.2. Necitumumab

Prior to each administration of necitumumab, all toxicities associated with necitumumab must have resolved to Grade ≤ 2 (except for alopecia and skin toxicity) or baseline. Pretreatment laboratory data may not be older than 72 hours (Day 1 of each cycle) or 24 hours (Day 8 of each cycle).

If the criteria are not met at the time of a planned treatment, the following general rules for the management of treatment delays apply:

- In the case of reversible Grade 3-4 necitumumab-related toxicity (for example, fatigue, anorexia, and fever), administration of necitumumab will be at the reduced dose (refer to [Section 9.4.1.2.2.1](#)) or interrupted, but pembrolizumab will continue according to the planned schedule.
- If administration of necitumumab is delayed for more than 6 weeks (2 cycles) after Day 1 of the most recent treatment cycle, the patient should be discontinued from necitumumab treatment.

9.4.1.2.2.1. Necitumumab Dose Modifications

The following are general dose-modification guidelines for toxicity associated with necitumumab. Please see [Section 9.4.1.3](#) for specific information on the management of necitumumab-related hypersensitivity/IRRs, skin reactions, conjunctivitis, and hypomagnesemia.

For patients starting Cycle 1 in Part A and possible Part B of the study at necitumumab 600 mg on Days 1 and 8, one dose reduction is permitted. Patients who cannot tolerate necitumumab 400 mg should discontinue necitumumab; such patients may continue with pembrolizumab as a single agent.

For patients starting Cycle 1 at dose level 800 mg on Days 1 and 8 in Part A and possible Part B and Part C of the study, 2 dose reductions are allowed following reversible CTCAE Grade ≥ 3 AEs that require delay of necitumumab treatment for up to 6 weeks following Day 1 of the most recent treatment cycle, unless DLT criteria are met (Cycle 1 Parts A and C). In this setting, necitumumab may be re-administered at a reduced dose (600 mg) if necessary only if AE is resolved to Grade ≤ 2 . A second dose reduction is permitted for this level of event (Grade ≥ 3). Necitumumab must be discontinued if further dose reduction is required beyond 400 mg on Days 1 and 8 Q3W. The patient may continue to receive pembrolizumab as a single agent.

Necitumumab dose adjustments are allowed both within a cycle and between cycles.

Necitumumab may be held up to 6 weeks (2 cycles) to permit sufficient time for recovery from the toxicity. If a dose delay occurs, the investigator may resume necitumumab dosing at the same dose level for the remainder of the study or at reduced dose (assuming resolution to at least Grade 1 for nonhematologic and at least Grade 2 for hematologic toxicity). If the patient experiences the same toxicity with the same or greater severity (CTCAE grade) requiring a dose delay within a cycle or at start of the next cycle, the patient must be dose reduced and not re-challenged a second time at the prior dose level.

If a patient experiences CTCAE Grade ≥ 3 hematologic toxicity possibly related to necitumumab, unless DLT criteria are met, then dosing must be delayed (until the toxicity resolves to either baseline or at least Grade 2) and the dose of necitumumab must be reduced by 1 dose level (see below).

If a patient experiences CTCAE Grade ≥ 3 nonhematologic toxicity possibly related to necitumumab, unless DLT criteria are met, then dosing must be delayed (until the toxicity resolves to either baseline or at least Grade 1) and the dose of necitumumab must be reduced by 1 dose level (see below).

For patients requiring dose reduction(s), any re-escalation to a prior dose level is permitted only after consultation with the Lilly CRP. After re-escalation, subsequent dose adjustments should be based on the dose of necitumumab that the patient is currently receiving. Following a dose reduction, the dose of necitumumab may be re-escalated to the pre-reduction dose, provided that at least 2 administrations of the reduced dose were given, and only after consultation with the Lilly CRP.

Table JFCQ.9.3. Dose Adjustments of Necitumumab

Dose Adjustment Level	I.V. Dose	Frequency
0	800 mg	Days 1 and 8 Q3W
-1	600 mg	Days 1 and 8 Q3W
-2	400 mg	Days 1 and 8 Q3W

Abbreviations: I.V. = intravenous; Q3W = every 3 weeks.

Events that necessitate more than 2 dose reductions warrant discontinuation from necitumumab treatment. For dose modifications in response to specific AEs related to necitumumab, please see Section [9.4.1.3](#).

Patients who enter the study with symptoms or laboratory values equivalent to NCI-CTCAE Version 4.0 Grade 1-2 AEs should not have dose reductions related to the persistence or mild worsening (for example, from Grade 1 to Grade 2) of those symptoms or laboratory values.

In the event of alterations of necitumumab therapy due to a necitumumab-related toxicity, pembrolizumab need not be altered, and the planned pembrolizumab schedule should be maintained. Similarly, necitumumab therapy should not be delayed for pembrolizumab-related toxicities.

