3	
 Administer topical clindamycin 2% and topical hydrocortisone 1% in lotion base twice daily to affected areas until resolution of reaction. Administer oral minocycline or doxycycline 100 mg twice daily (or equivalent), for a minimum of 4 weeks and continuing for as long as rash is symptomatic. Patients are advised to take appropriate protective measures prior to sun exposure to avoid exacerbation of rash severity. Necitumumab administration will be temporarily withheld until symptoms resolve to Grade ≤ 2, but not for longer than a maximum of 6 weeks following Day 1 of the most recent treatment cycle. Following improvement to Grade ≤ 2, necitumumab may be re-administered, with a dose reduction of 50% but not below 400 mg. This dose may be increased to 75% of the original dose) after a minimum of 1 treatment cycle (3 weeks), if symptoms do not recur. If symptoms do not recur for another treatment cycle, the dose may be re-escalated to the initial dose). If reactions do not resolve to Grade ≤ 2 after 6 weeks (that is, after withholding 2 consecutive doses of necitumumab), or if reactions recur or become intolerable at 50% of the original dose, necitumumab treatment should be permanently discontinued. Patients who experience Grade 3 skin induration / fibrosis will be immediately discontinued from necitumumab.
4	
 Administer topical clindamycin 2% and topical hydrocortisone 1% in lotion base twice daily to affected areas until resolution of reaction. Administer oral minocycline or doxycycline 100 mg twice daily (or equivalent), for a minimum of 4 weeks and continuing for as long as rash is symptomatic. Patients are advised to take appropriate protective measures prior to sun exposure to avoid exacerbation of rash severity. Necitumumab administration must be immediately and permanently discontinued.

If necitumumab therapy is delayed due to acneiform rash, pembrolizumab may be administered without interruption in the absence of disease progression.

A dermatology referral may be indicated for skin reactions that do not improve following 1-2 weeks of treatment, reactions that are severely symptomatic (for example, necrosis, blistering, or petechial or purpuric lesions), reactions of NCI-CTCAE Grade ≥ 3 , or reactions with an uncharacteristic appearance.

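### After a recurrent necitumumab toxicity, one rule bars return to the earlier dose and a later paragraph of the same section allows it; the skin table's step-ups omit the consultation required for any re-escalation

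*Protocol*

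**What the plan says.** Three pieces of protocol text bear on the necitumumab dose after a toxicity.

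- **The bar (Section 9.4.1.2.2.1).** After a first delay, "the investigator may resume necitumumab dosing at the same dose level for the remainder of the study or at reduced dose". The next sentence covers recurrence: "If the patient experiences the same toxicity with the same or greater severity (CTCAE grade) requiring a dose delay within a cycle", or at the start of the next one, then "the patient must be dose reduced and not re-challenged a second time at the prior dose level". It names no exception and no consultation route.
- **The re-escalation paragraph (same section, further down).** For patients who have been reduced, "any re-escalation to a prior dose level is permitted only after consultation with the Lilly CRP". It adds that "the dose of necitumumab may be re-escalated to the pre-reduction dose, provided that at least 2 administrations of the reduced dose were given", again with consultation. Nothing separates reductions made for a recurrence from other reductions.
- **The skin table (Section 9.4.1.3.2.1, Table JFCQ.9.6, Grade 3 row).** Once the reaction has improved, "necitumumab may be re-administered, with a dose reduction of 50% but not below 400 mg". The dose may rise to 75% of the original "after a minimum of 1 treatment cycle (3 weeks), if symptoms do not recur". Then: "If symptoms do not recur for another treatment cycle, the dose may be re-escalated to the initial dose". Consultation is not mentioned. Recurrence or intolerability at the 50% dose means permanent discontinuation.

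The general section calls its rules general guidelines and refers to Section 9.4.1.3 for skin reactions and other specific events. It also says that events needing more than two dose reductions warrant stopping necitumumab, and Section 7.3.2 repeats that limit.

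**The concern.** A patient reduced because a toxicity recurred has had a dose reduction. The bar closes the earlier dose to that patient; the re-escalation paragraph opens it again. Both sentences are in one section, so the referral to Section 9.4.1.3 cannot decide between them.

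A second, separate mismatch concerns who must be asked. The general section requires sponsor consultation for every re-escalation, but the skin table describes two step-ups without it. One site could consult and another could go ahead alone, each pointing to protocol text.

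At stake is the dose given to someone who has just had the same toxicity twice. Reporting is also touched: SAP Section 5.6.1.1 summarises necitumumab dose intensity and reductions, and SAP Section 5.4 makes more than two reductions an important protocol violation.

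**Working it through.** The plan states no figure on this point, so the check is a comparison of texts with simple dose arithmetic.

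**Inputs.** Dose levels are 800, 600 and 400 mg on Days 1 and 8 of a 21-day cycle (Table JFCQ.9.3), so a full cycle has 2 planned infusions.

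**Step 1: follow one patient through the general section.** A patient starts at 800 mg, has a toxicity that delays dosing, and resumes at 800 mg. The same toxicity returns at the same grade and forces another delay. The dose is reduced to 600 mg. After Day 1 and Day 8 at 600 mg, two infusions have been given.

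| Text | May the patient return to 800 mg? |
|---|---|
| Bar | No |
| Re-escalation paragraph | Yes, after consultation |

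The section also requires a one-level reduction after a related Grade 3 or higher toxicity (unless it meets DLT criteria), which narrows the same-dose route. The question arises by another route too: reduced to 600 mg, re-escalated to 800 mg after consultation, then the same toxicity recurs. The two texts again answer differently.

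**Step 2: size of the difference.**

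- At 800 mg: 800 × 2 = 1600 mg per cycle.
- At 600 mg: 600 × 2 = 1200 mg per cycle.
- Difference 400 mg per cycle; ratio 1600 / 1200 = 1.33.

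**Step 3: consultation.** From 800 mg, the skin table's 50% is 400 mg and its 75% is 600 mg, followed by 800 mg. Its minimum of one cycle per step contains two planned infusions, so that wait is compatible with the general section's two-infusion condition unless a Day 8 dose is omitted. The mismatch is the consultation, required by one text and absent from the other.

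**Step 4: recurrence of a Grade 3 skin reaction, 800 mg starter.**

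| Dose at recurrence | Table JFCQ.9.6 | General section |
|---|---|---|
| 400 mg (50%) | Stop permanently | Also stop if a reduction below 400 mg would be needed |
| 600 mg (75%) | Silent | Bar: reduce, no second return. Re-escalation paragraph: return possible after consultation |
| 800 mg (initial) | Silent | The same two answers |

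So there is no collision at the 50% dose; it lies above it. The two-reduction limit may supply a further answer there. Going from 800 to 400 mg is already two levels down, and the protocol does not say whether the count starts again after a re-escalation.

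**Step 5: primary analysis.** The response-rate test (SAP Section 5.5.5) rests on 54 evaluable patients and rates of 20% and 35%, with no dosing input. An exact binomial rule requiring at least 16 responders gives one-sided alpha 0.060 and power 0.834, in line with the stated limits of 10% and 83%. This finding changes none of that.

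**The case against.** The best defence is that the texts can be read together. The bar sits in the paragraph on resuming after a delay and may forbid only another direct resumption at that level. Re-escalation is a later event, optional, and subject to two infusions and consultation. Alternatively, the mandatory bar is a specific exception to a general permission. Each reading is reasonable, and on either one the conflict becomes an ambiguity. But the first lets the patient return to the earlier dose and the second does not, and the protocol does not choose.

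On the skin table, the defence is that the general section sends the reader to Section 9.4.1.3, so the table governs the skin-specific steps, and its silence on consultation waives nothing. A site can satisfy both texts by consulting. That stands as a way to comply, but the protocol never says that the requirement carries over.

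Three stronger readings might be inferred, and the documents do not support them.

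- **That the skin table raises the dose on elapsed time alone, or after a recurrence.** Each step-up requires that symptoms have not recurred, and recurrence at 50% ends necitumumab.
- **That the sequence can repeat without limit.** Sections 7.3.2 and 9.4.1.2.2.1 set a limit of two reductions, although how it is counted after a re-escalation is unstated.
- **That about 4 to 8 of 54 patients would be affected.** That comes from 0.082 × 54 = 4.4 and 0.141 × 54 = 7.6, using the Grade 3 or higher skin rates for SQUIRE and INSPIRE in Section 5.2. Those rates count any such event under first-line chemotherapy combinations, not a recurrence that forces a delay.

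**Conclusion.** The point holds as an unreconciled pair of rules within Section 9.4.1.2.2.1, plus a consultation requirement that Table JFCQ.9.6 does not carry and a gap in that table for recurrence above the 50% dose. For an 800 mg starter whose toxicity recurs at 800 mg and who is reduced one level, the readings differ by one third in drug per cycle (1600 versus 1200 mg).

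That figure assumes both planned infusions are given in each cycle. It says nothing about how often the situation arises: the documents give no rate of recurrent toxicity, so the number of patients is unknown. Differences between sites in exposure or dose intensity are possible but not shown. The matter deserves correction because it concerns a safety-relevant dosing step. It is not a flaw in the design or in the primary test.

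**What to change.** Reconcile the passages in protocol Sections 9.4.1.2.2.1 and 9.4.1.3.2.1 so that they give one answer to each of these questions:

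- (a) Is re-escalation available after a reduction made because a toxicity recurred?
- (b) Does the consultation requirement apply to the step-ups in Table JFCQ.9.6?
- (c) Which passage governs when a skin reaction recurs above the 50% dose, and how does the two-reduction limit count after a re-escalation?

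The answers are for the sponsor's clinical team; no dose or clinical rule is proposed here. The cost is amendment wording, with no change to the sample size or the primary analysis.

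### For some Grade 3 or higher necitumumab-related toxicities, the protocol contradicts itself on the recovery grade for re-treatment and on whether dose reduction is optional or compulsory

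*Protocol*

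**What the plan says.** **Recovery grade.** Protocol 9.4.1.2.2 sets a condition before each administration: "all toxicities associated with necitumumab must have resolved to Grade ≤ 2 (except for alopecia and skin toxicity) or baseline". It does not separate hematologic from nonhematologic toxicity. In 9.4.1.2.2.1, the paragraph for patients starting at 800 mg deals with reversible Grade 3 or higher events and uses the same grade: "necitumumab may be re-administered at a reduced dose (600 mg) if necessary only if AE is resolved to Grade ≤ 2".

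Further on in 9.4.1.2.2.1, the sentence on resuming after a delay splits the threshold: "assuming resolution to at least Grade 1 for nonhematologic and at least Grade 2 for hematologic toxicity". Two paragraphs then deal with Grade 3 or higher events possibly related to necitumumab. Hematologic toxicity must wait "until the toxicity resolves to either baseline or at least Grade 2", and nonhematologic toxicity "until the toxicity resolves to either baseline or at least Grade 1".

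**Dose on resumption.** After a delay, "the investigator may resume necitumumab dosing at the same dose level for the remainder of the study or at reduced dose". If the same toxicity recurs at the same or greater severity and again requires a delay, "the patient must be dose reduced and not re-challenged a second time at the prior dose level". The two paragraphs on Grade 3 or higher events nevertheless make both a delay and a one-level reduction compulsory, for hematologic and nonhematologic toxicity alike.

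**Delay.** A bullet in 9.4.1.2.2 says that for reversible Grade 3-4 toxicity necitumumab is either given at the lower dose or interrupted.

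**The concern.** A patient whose nonhematologic toxicity has improved from Grade 3 to Grade 2 meets the re-treatment condition in two places and fails it in two others. When that patient does resume, the dose is the investigator's choice under one sentence and fixed under another. The protocol does not say which wording governs.

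Four things are at stake:

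- **Patient safety and consistency.** Patients in the same clinical state may be dosed at one site and held at another, or resumed at different doses.
- **Discontinuation.** A patient who stays at Grade 2 beyond the 6-week limit leaves necitumumab under one wording but could have been dosed under the other. A 600 mg starter is allowed only one reduction, so whether the first Grade 3 event forces it decides when that allowance is used up.
- **Exposure summaries.** SAP 5.6.1.1 reports necitumumab dose reductions, delays and relative dose intensity. These would partly reflect which sentence each site followed.
- **DLT status.** Protocol 9.4.1.1 counts as a DLT a failure, due to toxicity, to give at least 75% of the planned Cycle 1 dose. Whether the Day 8 dose is given or withheld can decide this.

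**Working it through.** The point rests on wording, and the plan has no figure to reproduce. I take a Grade 3 or higher necitumumab-related toxicity that has no rule of its own in 9.4.1.3 and does not meet DLT criteria, and apply each passage to it. I read resolution to at least Grade 1 as Grade 1 or lower, and likewise for Grade 2.

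| Question | One wording | Other wording | Result |
|---|---|---|---|
| Nonhematologic toxicity, now Grade 2: may the patient be re-treated? | Condition met: 9.4.1.2.2; 800 mg paragraph of 9.4.1.2.2.1 | Condition not met (unless Grade 2 was baseline, which one sentence allows): two later sentences of 9.4.1.2.2.1 | Conflict |
| Hematologic toxicity, now Grade 2: may the patient be re-treated? | Condition met in all places | None | Consistent |
| Dose at first resumption, either type | Same or reduced, by choice; or reduced only where necessary (800 mg paragraph) | One-level reduction compulsory | Conflict |
| Must dosing be delayed? | Lower dose or interruption (9.4.1.2.2) | Delay compulsory (9.4.1.2.2.1) | Ambiguous |

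The recovery-grade conflict lies inside 9.4.1.2.2.1 as well as between the two sections. On dose, the recurrence sentence forbids a second re-challenge at the prior level. That implies one same-dose re-challenge is allowed, which the compulsory reduction rules out for Grade 3 or higher events.

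**Consequence for DLT status.** Take a patient in Part A, Cohort 2 with Grade 3 fatigue in Cycle 1 that improves to Grade 2 by Day 8 and stays there. Under 9.4.1.1, Grade 3 or higher fatigue lasting less than 7 days with full supportive therapy is not itself a DLT. Under 9.4 the Day 8 dose may be delayed by up to 5 days and is then omitted.

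- Planned Cycle 1 necitumumab: 2 × 800 = 1600 mg.
- Grade 2 wording, Day 8 given at 600 mg: (800 + 600) / 1600 = 87.5%.
- Grade 2 wording, Day 8 given at 800 mg: 1600 / 1600 = 100%.
- Grade 1 wording, Day 8 omitted: 800 / 1600 = 50%, below 75%.

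For a 600 mg starter the corresponding figures are (600 + 400) / 1200 = 83.3% and 600 / 1200 = 50%. In either cohort the same patient can be a DLT or not, depending on the sentence followed. This assumes that the 7 days count time at Grade 3 or higher, and that the 75% criterion is judged for each agent separately. Under 8.1, 2 or more DLTs among 6 in Cohort 2 make the Cohort 1 dose the MTD, and 2 of 6 in Part C trigger a sponsor review. One reclassified patient could therefore matter.

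**The case against.** **The stricter rule simply prevails.** Both Grade 2 statements are worded as necessary conditions, so a site that waits for Grade 1 breaches neither, and a site that always reduces breaches nothing in the sentence giving a choice. That is logically sound, and a consistent path through the text exists. It does not remove the conflict. No precedence is stated, the 800 mg paragraph addresses the same Grade 3 or higher setting and can be read as permission to dose at Grade 2, and a sentence that grants discretion cannot stand beside one that removes it.

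**The optional sentence covers only milder events.** The text does not say so. Under 9.4.1.2.2, toxicity at Grade 2 or lower does not generally block dosing. The delays in question are therefore largely the Grade 3 or higher events to which the compulsory rule applies.

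**A reduced dose with no delay.** A reader might infer that 9.4.1.2.2 permits this outright, in direct conflict with the compulsory delay. The documents do not support that. The bullet sits under rules for managing treatment delays and follows a bar on dosing until recovery. The wording is ambiguous and should be cleared up in the same edit, but it is not a clear waiver of the delay.

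**The DLT route is narrow.** This stands. Most related Grade 3-4 nonhematologic toxicity in Cycle 1 is already a DLT under 9.4.1.1. The 75% criterion decides the matter only for the toxicities excepted there.

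**Conclusion.** The contradiction is real on two points: the recovery grade for nonhematologic toxicity, and whether the dose at first resumption must be reduced, for both toxicity types. It applies to Grade 3 or higher necitumumab-related events outside the event-specific rules and not meeting DLT criteria. The hematologic threshold, the dose ladder in Table JFCQ.9.3 and the 6-week limit are consistent, and the ORR sample size and test are untouched.

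Three stronger readings should be resisted.

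- *Dosing after toxicity is undefined.* It is defined, but inconsistently, for a subset of events.
- *Every nonhematologic Grade 3 or higher event is affected.* Skin reactions have their own withholding and reduction rules in Table JFCQ.9.6, Grade 3-4 infusion reactions end necitumumab under Table JFCQ.9.4, and events meeting DLT criteria are excepted.
- *About 6 to 14 of 60 patients are affected.* A reader could get this by applying the related Grade 3 or higher rates in Study JFCE (Protocol 5.2) to the 54 Part B patients plus 6 from Cohort 2: 0.103 × 60 ≈ 6 and 0.226 × 60 ≈ 14. Those rates include acne (own rule) and anemia (no threshold conflict), and come from weekly and 2-weekly schedules at 100 to 1000 mg. In Study JFCA, the two cohorts on this trial's Days 1 and 8 schedule had no related Grade 3 or higher event in 3 + 6 = 9 patients, too few to settle a rate. All these figures count patients with an event, not patients for whom the rules diverge.

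The affected set need not be empty. Fatigue, an example named in 9.4.1.2.2, was a related Grade 3 or higher event in 4 of 60 JFCE patients. No firm count can be derived.

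**What to change.** The sponsor should reconcile 9.4.1.2.2 and 9.4.1.2.2.1 so that they give one recovery grade for each toxicity type and one statement on whether delay and dose reduction are required or optional after Grade 3 or higher toxicity. Alternatively, the protocol should state which passage takes precedence. The same edit should settle the bullet on a lower dose or interruption. Which rule is right is for the sponsor to decide.

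The cost is a protocol wording amendment and notice to sites. No change to the sample size or the primary analysis is needed.
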